The main body of evidence regarding the efficacy and safety of prophylactic topical epinephrine for the prevention of superficial hemorrhage is derived from the surgical literature, specifically endoscopic endonasal and sinus surgery, rhinoplasty, and surgical management of burn injuries. During functional endoscopic sinus surgery (FESS) and rhinoplasty, common practice involves administration of topical vasoconstrictor in the form of 1:1,000 epinephrine-soaked neuropatties as well as intranasal injection of a mixed solution of local anesthetic and 1:100,000 epinephrine (69). A recent randomized controlled trial comparing cocaine- and epinephrine-soaked neuropatties in 37 patients found no significant difference in blood loss with cocaine as compared to epinephrine. In this study, no adverse effects associated with cocaine or epinephrine were documented (70). A non-randomized trial comparing cocaine with epinephrine in 65 patients undergoing rhinoplasty showed similar results (71). The reported rate of cardiovascular complications associated with topical epinephrine in this patient population is 0.1% or less (72,73) with no deaths reported. In a series of 1,998 patients undergoing endoscopic sinus surgery in which 1:1000 diluted topical epinephrine was used for hemostatic purposes, Orlandi *et al.* reported two complications likely associated with the use of topical epinephrine (<0.1%). Once case involved ECG changes and the other case involved intraoperative hypertension due to inadvertent submucosal injection of the epinephrine solution (73). In a more recent prospective series of 19 patients undergoing the same surgery using epinephrine at the same dilution of 1:1000, there were no documented cases of altered hemodynamics related to topical application of epinephrine (74). A study in 10 burn patients undergoing burn wound excision using 1:10000 diluted epinephrine-soaked gauze wrappings, did not show a significant increase in intraoperative serum concentration of epinephrine to indicate systemic absorption (75). Nonetheless, a different study in burn patients has demonstrated that tachycardia was more common in burn patients undergoing surgery where 1:10,000 epinephrine-soaked gauzes were used (76). This finding can be related to the relatively large interface between the applied

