In the PROPHET trial, we intend to assess the degree of biopsy-related bleeding, measures taken to control bleeding, and potential effects of bleeding on completion of the intended procedure in 100 bronchoscopy procedures performed on single and double lung transplant recipients, randomized to prophylactic topical epinephrine versus placebo (normal saline). The study participant, physician performing the TBLB, and independent observer reviewing the procedure recording will all be blinded to the randomization. Further use of measures to control bleeding that occurs during the procedure as well as the decision to complete the procedure as planned or to abort it prematurely will be left to the discretion of the performer. In this way, we aim to elucidate a potential role of topical epinephrine in the prevention of TBLB-related airway bleeding in lung transplant recipients and assess whether the dose and volume of instillation used in our institution comprises an effective means to prevent hemorrhagic complications of TBLB.

HYPOTHESIS

We hypothesize that prophylactic instillation of topical epinephrine prior to performance of TBLB will decrease the frequency and extent of biopsy-related hemorrhage as well as result in fewer procedures being aborted earlier than intended due to bleeding complications as well as shorter overall procedure time due to the preventive effect on bleeding. Concomitantly, we hypothesize that the instillation of topical epinephrine will not be associated with a serious adverse event profile in comparison to placebo.

SPECIFIC AIMS

In this randomized-controlled double blind placebo controlled clinical trial post-lung transplant patients scheduled to receive bronchoscopy with TBLB as part of their routine standard of care will be randomized to receive a fixed dose and volume of topical endobronchial epinephrine versus matching volume of placebo which will be instilled into the target biopsy airway prior to performance of TBLB. Our study will specifically aim at providing the following information:

Aim 1: Demonstrate the feasibility of assessments of bleeding related to TBLB, including:

1. The degree of TBLB-related bleeding using a standardized grading scale used by the physician performing the procedure to quantify the degree of procedure-related bleeding.

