2. The degree of TBLB-related bleeding using a standardized grading scale used by two independent observers blinded to patient data and study drug assignment who will review a video recording of the procedure to quantify the degree of procedure-related bleeding.
3. The magnitude of inter-observer variability in grading TBLB-related hemorrhage based on review of video recording of the procedure.

Aim 2: Evaluate the hypothesis that prophylactic administration of topical epinephrine results in reductions in TBLB-related hemorrhage in lung transplant recipients, including:

1. The frequency of active measures taken to control pulmonary hemorrhage once it occurred.
2. The proportion of procedures completed as planned in terms of obtaining a predefined target number of biopsy specimens.
3. Comparison between single- and double-lung transplant recipients in terms of prevalence and degree of TBLB-related hemorrhage.
4. Identification of clinical factors associated with an increased or decreased risk of procedure-related hemorrhage.

Aim 3: Evaluate the hypothesis that prophylactic administration of topical epinephrine affects the overall efficiency of bronchoscopy with TBLB performance, including:

1. Overall duration of the bronchoscopic procedure.

2. The proportion of procedures completed as planned in terms of number of adequate biopsies obtained as assessed by the physician performing the bronchoscopy.
3. The proportion of procedures resulting in acquisition of adequate biopsy samples that allows proper pathologic evaluation of assignment of a pathologic diagnosis.

Aim 4: Explore the hypothesis that instillation of our prespecified dose and volume of topical epinephrine into the target biopsy airway is not associated with an adverse event profile that is significantly different from placebo, including:

1. The prevalence of clinically significant hemodynamic changes.
2. The prevalence of cardiac adverse events, including conduction abnormalities, arrhythmia, and myocardial ischemia.
3. The prevalence of other vascular adverse events, including stroke, mesenteric ischemia, and critical limb ischemia.
4. Identification of clinical factors associated with an increased or decreased risk of drug-related adverse events.

STUDY PROTOCOL

Overview

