Informed Consent will be performed on the day of study recruitment. Eligible PROPHET Study patients will be discretely approached by one of the study investigators who will explain in layman's language the aims, methods, potential benefits, and hazards associated with participation in the PROPHET trial. Details of the protocol will be discussed with the potential participant at the time of scheduling the bronchoscopy procedure, ensuring adequate time for consideration of the protocol (>24 hours from initial discussion). These individuals will then be approached with the informed consent form. Whenever possible, the informed consent form will be given to the potential participants in advance. The risks, benefits, and alternative will be discussed so that the decision to participate in the study will be made independently by the candidate. Only a well-trained clinical coordinator, the principal investigator, or an associate investigator from the Division of Pulmonary and Critical Care Medicine in UMMC will obtain consent. The consent will be obtained using and Institutional Review Board (IRB) approved consent document.

Any potential participants who cannot consent for themselves will be excluded from the study, as defined by the exclusion criteria (see above). This includes anyone who will be, or will have been, in a stressful, painful, or drugged condition before or during the consent process or otherwise lacks the mental capacity to consent for themselves. We will not obtain consent from Legally Authorized Representatives (LARs). We will not enroll minors.

Lung transplantation recipients undergo multiple bronchoscopic procedures in the post-transplantation period. Hence, it is very likely that a patient who is eligible for participation in the

study will undergo more than one bronchoscopy with TBLB during the study period. In this instance, a separate informed consent will be obtained for each individual procedure.

Initial Evaluation

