Moderate	Any bleeding originating from the biopsy target airway requiring in addition to maneuvering the bronchoscope application of iced saline or topical epinephrine or placing the patient with the bleeding lung in the dependent position
Severe	Any bleeding originating from the biopsy target airway requiring, in addition to the above-mentioned maneuvers, early termination of the procedure or necessitating application of balloon tamponade, endotracheal intubation, application of a bronchial blocker, or use of other invasive measures to achieve hemostasis, such as bronchial artery embolization or surgical intervention

4. Number of forceps passes performed.
5. Number of adequate tissue samples obtained.

6. Early termination of the procedure due to bleeding complication, defined as non-achievement of the target number of tissue samples as designated by the performing bronchoscopist prior to the procedure related to hemorrhage.
7. Duration of the procedure from first bronchoscope insertion to last bronchoscope withdrawal.
8. Total volume of iced saline used during the procedure.
9. Total dose of unblended topical epinephrine used during the procedure.
10. Any use of hemostatic procedures including balloon tamponade, endobronchial blocker, bronchial artery embolization, emergency surgery.
11. Any use of devices or procedures with intention of securing the airway including oral airway, nasal airway, laryngeal mask, endotracheal intubation, emergency cricothyroidotomy, and emergency tracheostomy.
12. Unplanned admission to the hospital or escalation in level of care within 48 hours of the procedure.
13. Pathologic diagnosis achieved.

Safety Outcomes

The safety of topical epinephrine administration and potential instillation-related adverse events will be derived from clinical monitoring, vital signs, and ECG recordings during and immediately following the procedure as well as from any clinical, laboratory, or radiologic investigations performed during or following the procedure. Complications deemed related to topical epinephrine administration and comprise the study safety outcomes include:

1. All-cause mortality within 3 hours of instillation of the study drug.
2. Acute cardiovascular event, including cardiac arrest, new onset chest pain, acute myocardial ischemia, pulmonary edema, acute ischemic stroke, critical limb ischemia, acute mesenteric ischemia, occurring within 30 minutes of instillation of the study drug.

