3. Acute closed angle glaucoma within 30 minutes of the instillation of the study drug.
4. New onset ECG changes suggestive of myocardial ischemia, including ST segment changes (defined: ≥ 1 mm ST segment elevation or ≥ 3 mm ST segment depression in ≥ 2 precordial or limb ECG leads that correspond together to one of the cardiac walls), new onset ventricular tachycardia, significant increase (≥ 10 per minute) in occurrence of ventricular ectopic beats, new onset supraventricular arrhythmia, new onset bundle branch block, and new onset 2nd or 3rd degree atrioventricular block, all occurring within 30 minutes of the instillation of the study drug.
5. Significant change in heart rate (defined as heart rate of >120 bpm and/or increase by ≥ 30 bpm above the baseline or heart rate <60 bpm and/or ≥ 30 bpm below the baseline) as recorded within 30 minutes of the instillation of the study drug.
6. Significant change in systolic blood pressure (defined as increase in systolic blood pressure >180 mm Hg and/or ≥ 40 mm Hg above the baseline; increase in diastolic blood pressure >110 mm Hg and/or ≥ 20 mm Hg above the baseline; or fall in systolic blood pressure <90 mm Hg and/or ≥ 20 mm Hg below the baseline) as recorded within 30 minutes of the instillation of the study drug.

Please refer to the section titled “Adverse Events Reporting and Data Monitoring” for further elaboration regarding reporting adverse events to the study monitoring committee. Please refer to the section titled “Adverse Events Reporting to the IRB” for further elaboration regarding reporting adverse events to the IRB.

Immediate Post-Procedure Surveillance

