Data are expressed as means with standard deviations, medians with interquartile range, percentages, and proportions as appropriate. Continuous outcome variables were visually examined for normality and outliers using histograms and scatter plots. The normal distribution was assessed with the Shapiro-Wilk test. Continuous variables were compared with the Student's t-test for normally distributed data with similar variance and the Mann-Whitney tests for non-normally distributed data. Proportions were compared using Chi-squared or Fisher's exact tests as appropriate. Statistical significance was set at $P<0.05$. All statistical analyses were performed based on original assigned groups and using Stata software, version 14 (Stata Corp LLC).

Potential Benefits

We hypothesize that prophylactic instillation of topical epinephrine prior to TBLB will reduce procedure-related hemorrhage, leading to lower rate of prematurely aborted procedure due to bleeding complications and higher yield of intended biopsies. The participants may, therefore, have direct benefit from participation if prophylactic topical epinephrine reduces the rate of procedure related hemorrhage in TBLB therefore avoiding early termination of procedure and more intended biopsies taken providing a higher diagnostic yield.

No financial reimbursements or incentive for participating in the PROPHET study will be provided.

Potential Risks and Discomforts

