The decision to perform bronchoscopy with TBLB will be based on clinical indications as a part of each study participant standard of care and not as a part of the research. Potential risks and discomfort of the bronchoscopy and TBLB themselves are no more than what the participant would undergo as a part of their post-transplantation bronchoscopy. These risks include hemorrhage related to the procedural maneuvers, respiratory distress, pneumothorax (i.e. collapsed lung). These complications are rare (less than <1% of all bronchoscopies) and can be expected in any bronchoscopy and TBLB. An experienced bronchoscopist and a well-trained staff such as ours are well trained to handle these potential complications in the controlled environment of the bronchoscopy suite. Bronchoscopic procedures performed in the UMMC bronchoscopy suite are usually performed under conscious sedation. Potential risks and discomforts of conscious sedation for our study participants are no more than what the participant would undergo for their post-transplantation bronchoscopy. Conscious sedation is generally safe, but can cause nausea and vomiting, ineffective ventilation resulting from airway obstruction or respiratory depression, causing hypoxia, hypercarbia, or aspiration associated with loss of protective airway reflexes, as well as cardiovascular complications including hypotension and arrhythmia. Drug overdose and drug reactions are a constant possibility in patients undergoing conscious sedation.

The potential risks of epinephrine are well described in cases of sufficient systemic absorption of the drug. Most serious complications are arrhythmias and hemodynamic compromise and tend to occur in a dose dependent manner. Most complications seen are in the setting of existing bleeding from procedural maneuvers. Topical epinephrine, in these situations, is instilled in airways with damaged mucosa and blood vessels. There is direct communication between the airway and blood vessels allowing for more direct absorption of epinephrine leading to higher concentration of epinephrine in the blood stream and therefore systemic complications. There²⁶ is no reported data of the incidence rate of complications arising from epinephrine in the setting of topical prophylactic use, but it is expected to have lower rate of systemic absorption. In rare

cases of complications, our staff is well trained and the procedure room is equipped to treat these potential complications of epinephrine.

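### Aim 4 words safety as the absence of a significant difference from placebo, with no between-arm interval or margin, in a trial small enough for a real excess to be missed often

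*Combined protocol and SAP*

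**What the plan says.** Aim 4, under Specific aims, sets out to explore whether instilling the study dose "is not associated with an adverse event profile that is significantly different from placebo". The Hypothesis section expects that epinephrine "will not be associated with a serious adverse event profile in comparison to placebo". Neither section says what result would count for or against the statement.

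The Safety Outcomes section lists the events. They run from rare and serious ones ("Acute cardiovascular event, including cardiac arrest, new onset chest pain, acute myocardial ischemia" and others) to threshold changes in vital signs and ECG (for example "Significant change in heart rate", with numerical limits and a 30-minute window).

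The Data Analysis section has one line that applies to these outcomes: "Proportions were compared using Chi-squared" or Fisher's exact tests as appropriate, with significance at P<0.05. Percentages and proportions will be shown. It names no risk difference, confidence interval or margin, and it does not say whether tests are one- or two-sided. The same section says that formal power calculations are not possible and that numbers rest on feasibility. The Overview plans 100 procedures in the final analysis.

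**The concern.** A non-significant test does not show that two arms are alike. It shows only that the data did not separate them, and a small trial often fails to separate arms that differ. As worded, Aim 4 is met by a large P-value, and the smaller the trial, the easier a large P-value is to obtain.

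What is at stake is the safety statement. A real excess of haemodynamic or cardiac events could be written up as not different from placebo mainly because there were few procedures. That matters for planning a larger trial. The Potential Risks and Discomforts section says that there "is no reported data of the incidence rate of complications arising from epinephrine in the setting of topical prophylactic use", so this trial's safety estimates would be among the first available. A reader needs to know how large an excess the data exclude, and a P-value does not say.

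**Working it through.** The plan gives no safety margin, power figure or safety-based sample size, so there is no stated figure to reproduce. The check asks how the only stated criterion behaves at the planned size.

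**Inputs**
- 100 procedures in total (Overview).
- Allocation by unrestricted coin toss (Study Group Randomized Assignment). A 50:50 split is therefore an expectation; its probability is C(100,50)/2^100 = 8.0%. A fair coin gives 40 to 60 per arm in the central 95%.
- Significance at P<0.05 (Data Analysis). Two-sided is assumed.
- Event rates for common vital-sign and ECG outcomes are not in the documents. The rates in step 1 are assumptions.

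**1. Chance of a non-significant result when there is a real excess**

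For each split n1:n2, sum Bin(a; n1, p1) × Bin(b; n2, p2) over all pairs (a, b) for which two-sided Fisher gives P≥0.05.

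| Assumed true rates, epinephrine vs placebo | Split | P(non-significant), Fisher |
|---|---|---|
| 20% vs 10% | 50:50 | 80.5% |
| 20% vs 10% | every split from 40:60 to 60:40 | 72.5% (42:58) to 80.5% (50:50) |
| 20% vs 10% | averaged over coin-toss splits | 76.6% |
| 40% vs 20% | 50:50 | 48% |

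If uncorrected chi-squared is used whenever all expected counts are at least 5, the 50:50 figures fall to 70% and 40%. The choice of test does not change the conclusion.

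**2. A case where the test and the interval disagree**

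Take 5 events on epinephrine and 0 on placebo, at exactly 50:50. The expected event count is 2.5 per arm, so Fisher is the appropriate test.
- Fisher: P = 2 × C(50,5)/C(100,5) = 2 × 2,118,760/75,287,520 = 0.056.
- Six against none: P = 2 × C(50,6)/C(100,6) = 0.027, the first significant result when placebo has no events.
- Newcombe 95% interval for the 5 vs 0 difference of +10 points. The Wilson limits are 4.35% to 21.36% for 5/50 and 0% to 7.13% for 0/50.
  - Lower limit: 0.100 − √[(0.100 − 0.0435)² + 0.0713²] = 0.100 − 0.091 = +0.9 points.
  - Upper limit: 0.100 + (0.2136 − 0.100) = +21.4 points.

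The interval excludes zero while the test is non-significant.

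This example depends on the split. At 49 epinephrine to 51 placebo, the mirror-image table (all five events on placebo) is more probable than the observed one, so it drops out of the two-sided sum and P = C(49,5)/C(100,5) = 0.025. At 51:49, P = 0.057. Over coin-toss splits, 5 vs 0 is non-significant about 54% of the time.

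**3. No events at all**

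The exact (Clopper-Pearson) two-sided 95% upper limit for 0 of n is 1 − 0.025^(1/n). For n = 50 this is 7.1%.

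The Topical Epinephrine for Bleeding Prophylaxis section gives a figure from sinus and nasal surgery ("The reported rate of cardiovascular complications associated with topical epinephrine in this patient population is 0.1% or less"), which may not transfer to this setting. The probability of 0 of 50 is (1 − r)^50: 95% if r = 0.1%, 61% if r = 1%, and 36% if r = 2%. Zero events would hardly tell these rates apart.

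**4. Repeat procedures**

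The consent section says it is very likely that a patient "will undergo more than one bronchoscopy with TBLB during the study period". The effect on the between-arm difference was simulated with 100 procedures, 1 to 5 per patient, each randomised separately, rates of 10% and 20%, and a patient random-intercept SD of 0 to 2 on the logit scale. The true standard error was 1.00 to 1.03 times the naive one.

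Per-arm limits are more sensitive. If 50 procedures carried the information of 40 or 25 independent ones (assumed values), the 7.1% limit would become 1 − 0.025^(1/40) = 8.8% or 1 − 0.025^(1/25) = 13.7%.

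**The case against.** The strongest reply is that this is a pilot, that Aim 4 only explores, and that the plan says openly that its numbers rest on feasibility. Event rates by arm are in effect already planned: Aim 4 speaks of prevalence, and the Data Analysis section reports percentages. The Safety Outcomes section defines events and time windows. The Data Monitoring section provides independent review after 40 procedures or 10 major bleeding events, and at least every six months afterwards. With counts and denominators reported, a reader could compute the missing interval.

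Much of this stands, and it lowers the severity. It does not remove the point. Pilot status argues for estimation and against a significance criterion. Monitoring protects participants but does not say how the arms will be compared in the report. Rates by arm without an interval do not show how uncertain the difference is.

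Three stronger readings are tempting, and the documents do not support them.
- A reader might infer that the plan commits to calling epinephrine safe whenever P≥0.05. It does not say so; it simply gives no other criterion.
- A reader might infer that 5 events against none would always be non-significant. That holds at 50:50 but fails at 49:51, and an exactly even split is not guaranteed.
- A reader might infer that repeat patients require clustered standard errors for the difference. The simulation shows almost no effect when each procedure is randomised separately, and such errors are unreliable with sparse events. The documents give no repeat fraction.

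**Conclusion.** The concern holds as a minor-to-moderate point on inference and reporting. The safety hypothesis is phrased so that a non-significant test fits it, no other criterion is offered, and the trial was not sized to detect harm. A doubling from 10% to 20% would be missed roughly three times in four by Fisher, and a doubling from 20% to 40% about half the time. For rare serious events, an empty arm of 50 excludes only rates above about 7%.

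These figures rest on assumed event rates, two-sided testing, splits within 40:60 to 60:40, and independent procedures. The 20% vs 10% result holds for every split in that range and for either test. The 5 vs 0 example is an illustration tied to one split and should not carry the argument. Nothing here implies that the trial is unsafe to run or that its safety data are inadequate.

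**What to change.** - Restate Aim 4 as estimation of the difference in adverse event rates, and bring the safety sentence in the Hypothesis section into line.
- For each item under Safety Outcomes, report the event rate by arm and the risk difference with a 95% interval suited to sparse counts, such as Newcombe.
- With zero or very few events, add an exact upper limit per arm.
- State in words the size of excess that the interval excludes.
- Pre-state that P≥0.05 will not be described as no difference or as safe.
- Report the number of distinct patients beside the number of procedures. A clustered interval for the difference is optional, as a sensitivity analysis only.

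The cost is a few sentences in Aim 4 and Data Analysis, and one interval or limit per outcome. It needs no new data and no change to sample size or conduct. The downside is a less favourable safety statement and a little more analysis work.
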